3.1 Confidence Intervals and P-values

The statistical uncertainty of all estimates will be expressed as two-sided 95% confidence intervals. A p-value will only be reported for all the primary and secondary outcomes. A p-value <0.05 will be considered significant.

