5.2 Analysis Methods

Unless otherwise specified, all analyses will be completed on the intention to treat population.

 CHU ANGERS <small>CENTRE HOSPITALIER UNIVERSITAIRE</small>	 Statistical analysis plan	N° EudraCT 2019-002145-37 CT Number : 2024-515994-83-00 SAP V1.0 Date : 15/01/2026
---	--	---

The characteristics at inclusion and the measures of patient assessments for each treatment arm will be described using percentages or means, standard deviations, medians and interquartile ranges, and compared using Khi-square tests or Student t tests for respectively categorical and continuous data. A summary of the proposed analyses is presented in Table 1.

5.2.1 Primary Outcome:

Primary analysis:

The main statistical analysis will be performed on the intention to treat population using a binomial logistic regression model including as covariates the treatment arm and the different stratification factors for randomization (the center, the initial WFNS score dichotomized as <3 vs ≥ 3 and the patient's consciousness at inclusion).

Secondary analysis:

As a secondary analysis, we will report absolute risk reduction using a proportional odds approach, using the Brant-Wald test at the alpha level of 5%, which may be more sensitive for detecting a shift over the entire spectrum of outcome (mRS 7-point ordinal scale).

Sensitivity analysis:

An other model will be proposed based on the ITT population, including in addition to the covariates already considered the level of consciousness and the delay before performing angiography (within 12 hours or not), and the interactions between these two covariates and the treatment arm, to assess a possible variation in the treatment effect according to the status on these two covariates

These two models will be performed on the per-protocol population as an evaluation of the robustness of their results. In any cases, the primary analysis results will be authoritative.

5.2.2 Secondary Outcomes:

- The analysis of the mRS, the extended GOS and the EQ-5D score at 3 and 6 months will be performed considering (ordinal) proportional odds models, based on the same set of covariates.
- The ICU mortality and 6 months mortality will be analyzed using Cox models based on the same set of covariates. The validation of these models will be evaluated by analyzing Schoenfeld residuals.

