5.3 Missing Data

First, every attempt will be made to retrieve the missing data. All missing data will be reported and the frequencies of these will be calculated.

A description of the patients characteristics depending on whether they have missing data or not will be proposed to distinguish missing completely at random or missing at random data.

 CHU ANGERS <small>CENTRE HOSPITALIER UNIVERSITAIRE</small>	 Statistical analysis plan	N° EudraCT 2019-002145-37 CT Number : 2024-515994-83-00 SAP V1.0 Date : 15/01/2026
---	--	---

In case of missing data, multiple imputations will be performed considering chained equations with fully conditional specification. The considered covariates included in this imputation process will include all covariates observed at the end-point evaluation (including the treatment allocation). Ten imputations will be performed for each missing data. This analysis will allow to calculate the Fraction of Missing Information (FMI), and then the Relative Efficiency (RE). If the RE ≥ 0.99 , then the number of imputations will be considered as appropriate. If not, the number of imputations will be determined as greater than the FMI value * 100 to ensure high relative efficiency.

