mRS at 3 month	Log-binomial logistic regression with fixed effects for treatment and, and a random effect for center, initial WFNS (<3 or ≥ 3) and patient's consciousness, reported as a risk ratio with 95% CI	
 Another model adjusted with level of consciousness and delay before performing arteriography (< or \geq 12h) Sub-group analysis Per protocol analysis† Patients without missing data 	
 Proportional odds analysis using the Brant-Wald test 	
 center, initial WFNS (<3 or ≥ 3) patient's consciousness at inclusion
Secondary outcomes				
mRS at 6-months	Log-binomial logistic regression reported as a risk ratio with 95% CI		
 unadjusted model Proportional odds analysis using the Brant-Wald test 	
 center, initial WFNS (<3 or ≥ 3) patient's consciousness at inclusion
GOSE at 3 and 6 months	Linear logistic regression model, reported as mean difference with 95% CI		
 unadjusted model 	
 center, initial WFNS (<3 or ≥ 3) patient's consciousness at inclusion
EQ-5D	Linear logistic regression model, reported as mean difference with 95% CI	
 Excluding deceased patient 	
 unadjusted model 	
 center, initial WFNS (<3 or ≥ 3) patient's consciousness at inclusion
Mortality hospital	Log-binomial logistic regression reported as a risk ratio with 95% CI		
 unadjusted model 	
 center, initial WFNS (<3 or ≥ 3) patient's consciousness at inclusion
Mortality 6 months	
 Kaplan-Meier curves and Cox regression hazard ratios 		
 unadjusted model 	
 center, initial WFNS (<3 or ≥ 3) patient's consciousness at inclusion
Tertiary outcomes				
ICU and Hospital LOS	Presented as median difference with 95% CI, using quantile regression		
 median with IQR unadjusted model 	
 center, initial WFNS (<3 or ≥ 3) patient's consciousness at inclusion

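### The ordinal mRS analysis names the Brant-Wald test, a check of proportional odds, where the treatment test belongs, and an absolute risk reduction without a cut-point.

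*SAP*

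**What the plan says.** Section 5.2.1 (Secondary analysis) describes the ordinal analysis of the 3-month mRS: "we will report absolute risk reduction using a proportional odds approach, using the Brant-Wald test at the alpha level of 5" per cent. The reason given is that it is an approach "which may be more sensitive for detecting a shift over the entire spectrum of outcome (mRS 7-point ordinal scale").

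Table 1 lists "Proportional odds analysis using the Brant-Wald test" under additional analyses, in both the 3-month and the 6-month mRS rows. It gives no effect measure for that analysis.

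Three other passages bear on the point:

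- Section 5.2.2 plans an ordinal model for the mRS without mentioning Brant-Wald: "The analysis of the mRS, the extended GOS and the EQ-5D score at 3 and 6 months will be performed considering" proportional odds models with the same covariates.
- Section 3.1 applies generally: "The statistical uncertainty of all estimates will be expressed as two-sided 95% confidence intervals". It also promises p-values for primary and secondary outcomes, with significance at p < 0.05.
- Section 5.2.1 limits the weight of everything but the main model: "In any cases, the primary analysis results will be authoritative".

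**The concern.** The Brant-Wald test compares the coefficients of the separate binary logits, one per cut-point of the scale. Its null hypothesis is that they are equal. A treatment that moves the whole mRS distribution by one common odds ratio satisfies that null exactly, however large the odds ratio. A small Brant-Wald p-value says that the single odds ratio summarises the data poorly; it is not evidence of benefit. Section 5.2.1 nevertheless gives this test the 5% level in an analysis meant to detect a shift, and names no other test there.

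The effect measure has a similar fault. The model estimates a common odds ratio. An absolute risk reduction can be derived from it, but only after choosing a cut-point and, in an adjusted model, a method of averaging over covariates. The SAP gives neither.

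At stake is the reporting of the only full-scale analysis of the primary endpoint. Two statisticians could report different p-values and different absolute figures, each claiming to follow the plan, and the cut-point could be chosen after the data are seen.

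**Working it through.** **Inputs from the SAP (sections 2.2 and 2.3).** Favourable outcome (mRS ≤ 2) 35% on control and 50% on milrinone; two-sided 5%; power 80%; 1:1 allocation; 170 per arm.

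**The plan's own figure.** With the normal approximation and pooled variance under the null, mean proportion 0.425:

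n = [1.96·√(2·0.425·0.575) + 0.8416·√(0.35·0.65 + 0.50·0.50)]² / 0.15² = (1.3703 + 0.5816)² / 0.0225 ≈ 169.3, rounded up to 170 per arm, 340 in total. This matches the SAP. Power of the binary comparison at 170 per arm is 80.2%.

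**Common odds ratio implied by the plan.** (0.50/0.50) / (0.35/0.65) = 1.857.

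**Assumed control distributions.** The SAP gives no mRS distribution, so three were assumed, all with 35% at mRS ≤ 2. Proportions for mRS 0 to 6:

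- A: .08/.12/.15/.14/.16/.10/.25
- B: .05/.10/.20/.20/.17/.13/.15
- C: .12/.13/.10/.10/.12/.08/.35

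**Which test responds to a uniform shift?** Unadjusted, 5,000 simulated trials per scenario, 170 per arm. Brant-Wald on the treatment term (six cut-points, 5 df) against a Wilcoxon score test of treatment, rejection at 5%:

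| | Brant-Wald, OR 1 | Brant-Wald, OR 1.857 | Treatment, OR 1 | Treatment, OR 1.857 |
|---|---|---|---|---|
| A | 4.8% | 5.1% | 5.1% | 90.7% |
| B | 4.0% | 4.2% | 5.6% | 89.8% |
| C | 4.8% | 5.3% | 5.5% | 90.4% |

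The simulation standard error near 5% is √(0.05·0.95/5000) ≈ 0.3 points. Brant-Wald barely changes between no effect and the planned effect.

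**With a Wald test of the common odds ratio.** A separate run of 10,000 trials per scenario, under slightly different assumed distributions (also 35% at mRS ≤ 2), gave 89.2 to 89.7% for that test and 4.8 to 5.0% for Brant-Wald under OR 1.857. With no effect, Brant-Wald rejected in 4.5 to 5.0%.

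**With covariate adjustment.** 1,200 trials per scenario, assuming 50% WFNS ≥ 3 (odds ratio 2.5) and 50% unconscious (odds ratio 3.0), center not simulated. A conditional treatment odds ratio of 2.0 reproduces 35% versus 50% marginally. Brant-Wald rejected in 4.9%, 5.8% and 5.4% (A, B, C); the likelihood-ratio treatment test in 94.5%, 94.8% and 94.1%.

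**What absolute risk reduction does one odds ratio give?** For control cumulative proportion c, the treated proportion is t = 1.857·c/(1−c) / [1 + 1.857·c/(1−c)], and the difference is t − c. Example, A at mRS 0: odds 0.08/0.92 = 0.0870; times 1.857 = 0.1615; t = 0.1615/1.1615 = 0.139; difference 5.9 points.

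| Cut-point | A | B | C |
|---|---|---|---|
| mRS 0 | 5.9 | 3.9 | 8.2 |
| ≤ 1 | 11.7 | 9.7 | 13.2 |
| ≤ 2 | 15.0 | 15.0 | 15.0 |
| ≤ 3 | 15.1 | 14.4 | 15.3 |
| ≤ 4 | 12.5 | 10.7 | 14.1 |
| ≤ 5 (alive) | 9.8 | 6.3 | 12.5 |

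Within one distribution the six figures span 5.9 to 15.1 (A), 3.9 to 15.0 (B) and 8.2 to 15.3 (C).

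**The case against.** The best defence is that the SAP, read as a whole, already supplies a treatment test. Section 5.2.2 plans a proportional odds model for the mRS at 3 and 6 months, such a model yields a common odds ratio and a test of treatment by construction, and section 3.1 asks for a confidence interval and p-value. On this view Brant-Wald is simply the assumption check, and the clause about sensitivity refers to the model. The only mRS dichotomy in the SAP is ≤ 2, so that is the natural cut-point. The simulation would then add little, because a rejection rate near 5% follows from the test's null.

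Much of this is fair. The model is sound and can detect a shift, and the near-5% rate is indeed a property of the test; the simulation only illustrates it. The power figures matter only if an analyst would report Brant-Wald as the treatment test.

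The defence does not remove the defect. For the Cox models, section 5.2.2 says that Schoenfeld residuals serve to validate the model; no such label is attached to Brant-Wald in 5.2.1 or in either Table 1 cell. Section 5.2.2 does not name the common odds ratio, and 5.2.1 names a different measure. The ≤ 2 cut-point is defined for the binary endpoint, and assuming it here sits badly with an analysis of the whole scale. Even if Brant-Wald was meant as a check, nothing says what follows if it rejects.

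**Conclusion.** The concern holds. As written, section 5.2.1 and both Table 1 cells attach the wrong test to the ordinal mRS analysis, and 5.2.1 names an effect measure that is undefined without a cut-point. The error lies in the named test and measure, not in the choice of model.

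Read literally, the 5% test would reject about as often with the planned effect as with none (4.2 to 5.3% against 4.0 to 4.8%, unadjusted), where a treatment test would reject in about 90%. The absolute figure could lie anywhere from 3.9 to 15.3 points for one and the same odds ratio. The power figures and the point range rest on assumed mRS distributions and a truly uniform shift; the adjusted figures also rest on assumed covariate effects without center. The near-5% Brant-Wald rate under a uniform shift does not depend on the assumed distributions.

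The consequence is limited. This is a supportive analysis, and neither the primary result nor the sample size is touched. It should be fixed, because the correction is nearly free and the present text lets the reported p-value and absolute figure be settled after the data are seen.

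**What to change.** Replace the secondary-analysis paragraph in section 5.2.1 with text such as:

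> Ordinal mRS (0 to 6) will be analysed with a proportional odds model including treatment arm and the minimisation factors. The treatment effect is the common odds ratio with its 95% CI and Wald p-value, pooled over the imputations of section 5.3. The Brant-Wald test is a diagnostic of the assumption only; the common odds ratio is reported whatever its result, with cut-point-specific odds ratios as a supplement. Any absolute risk difference is for mRS ≤ 2, obtained by standardisation from the adjusted model.

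In both Table 1 cells write: *Proportional odds model, common odds ratio with 95% CI (Brant-Wald as diagnostic)*.

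Some of this is a choice. A named fallback model could replace reporting the common odds ratio regardless of the diagnostic, and the absolute difference could be dropped, since the primary analysis already addresses mRS ≤ 2. What matters is that one rule is fixed in advance. The text should also say how center enters (a covariate in 5.2.1, a random effect in Table 1) and how the diagnostic is computed with imputed data.

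The cost is one paragraph and two table cells, with no extra data and no change to the sample size or primary analysis. Section 2.4 places publication of the SAP before database lock and unblinding after the primary and secondary analyses. If that sequence has been kept, the correction can be made blind; the document does not show whether lock has already occurred.

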1.2 Objectives

1.2.1 Primary objective

The primary objective of this study is to evaluate the effect of intravenous milrinone infusion, as compared with placebo, on functional neurological outcomes at 3 months in patients with arterial vasospasm following acute aSAH.

1.2.2 Secondary objectives:

To evaluate the effect of IV milrinone vs placebo on a) 3 and 6 months overall function; b) 3- and 6-months quality of life, c) mortality.

 CHU ANGERS <small>CENTRE HOSPITALIER UNIVERSITAIRE</small>	 MiVAR Statistical analysis plan	N° EudraCT 2019-002145-37 CT Number : 2024-515994-83-00 SAP V1.0 Date : 15/01/2026
---	--	---

1.2.3 *Tertiary objectives:*

To evaluate the effect of IV milrinone vs placebo on the intensive care unit (ICU) and hospital length of stays, on angiographic success at D7 and D14 (if available), on cerebral necrotic volume assess by magnetic resonance imaging (MRI) between 3 and 6 months following aSAH (if available) and on adverse events.

2 Section 2: Study Methods

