- b) Percentage of patients alive and at home at 3 and 6 months. It will also be analyzed as the number of days alive and at home at day 90 (DAAH90).
- c) angiographic success will be assessed by the evaluation of vasospasm severity on inclusion, D7 and D14 (if available) CTA. Vasospasm will be quantified according to the reduction of cerebral arteries diameter evaluated on a semi-quantitative scale as: absent, light, mild, moderate or severe, (compared to the diameter measured on admission CTA).
- d) Number of therapeutic arteriography
- e) The volume of cerebral necrosis will be measured on magnetic resonance imaging (MRI) obtained between 3 and 6 months following aSAH
- f) on adverse events evaluated until 48 hours after study medication stop.
- g) The treatment tolerance will be evaluated by assessing the rate of patients with hemodynamic intolerance defined as the need for catecholamines introduction or doses increased by 50% within the first 24 hours of study medication infusion ; and of metabolic intolerance defined as the rate of patients with dysnatremia, (ie natremia<135 mmol/L or >155 mmol/L) occurring during the administration of study medication.

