 CHU ANGERS <small>CENTRE HOSPITALIER UNIVERSITAIRE</small>	 Statistical analysis plan	N° EudraCT 2019-002145-37 CT Number : 2024-515994-83-00 SAP V1.0 Date : 15/01/2026
---	--	---

5.2.3 *Tertiary outcomes*

- The analysis of angiographic successes at day 7 and 14 will be performed considering (ordinal) proportional odds models, based on the same set of covariates
- The proportion of therapeutic arteriography between each group and the median number of arteriography will be compared.
- The analysis of hospital length of stay will be carried out by using linear regression models based on the same set of covariates.
- Patients outcomes and treatment tolerance will be analyzed using logistic models for dichotomous data (transfer to a convalescent center, patients living at home at 3 and 6 months, need to initiate or to increase the catecholamine doses by 50%, occurrence of dysnatremia), or linear regression models for continuous data (DAAH90, daily dose of catecholamines, average daily urine output).

5.2.4 *Pre-planned sub-group analysis*

We plan exploratory subgroup analyses for the primary outcome (as described above) in the following sub-groups:

- Sex: female sex versus male sex. We hypothesize no treatment effect difference between male and female sex.
- Initial WFNS score <3 vs ≥ 3 . We hypothesize that the treatment effect is more important in the less severe patients (WFNS <3).
- Consciousness level at inclusion: conscious vs unconscious. We hypothesize that the treatment effect is more important in the less severe patients (conscious patients).

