Percentage of patients alive and at home at 3 and 6 mnths	Presented as median difference with 95% CI, using quantile regression		
 median with IQR unadjusted model 	
 center, initial WFNS (<3 or ≥ 3) patient's consciousness at inclusion
DAAH90	Presented as median difference with 95% CI, using quantile regression		
 median with IQR unadjusted model 	
 center, initial WFNS (<3 or ≥ 3) patient's consciousness at inclusion
Angiographic success at D7 and D14	Ordinal logistic regression model		
 unadjusted model 	
 center, initial WFNS (<3 or ≥ 3) patient's consciousness at inclusion

 CHU ANGERS <small>CENTRE HOSPITALIER UNIVERSITAIRE</small>	 Statistical analysis plan	N° Eudract 2019-002145-37 CT Number : 2024-515994-83-00 SAP V1.0 Date : 15/01/2026
---	--	---

Number of therapeutic angiography	Presented as median difference with 95% CI, using quantile regression		
 Median with IQR unadjusted model 	
 center, initial WFNS (<3 or ≥3) patient's consciousness at inclusion
volume of cerebral necrosis on MRI done between 3 and 6 months	Presented as median difference with 95% CI, using quantile regression		Median with IQR	
Proportion of patient with hemodynamic intolerance (i.e. introduction of catecholamine or increase of ≥50% of infusion rate) within 24 hours of study medication	Log-binomial logistic regression reported as a risk ratio with 95% CI		
 unadjusted model 	
 center, initial WFNS (<3 or ≥3) patient's consciousness at inclusion
Proportion of patients with dysnatraemia	Log-binomial logistic regression reported as a risk ratio with 95% CI		
 unadjusted model 	
 center, initial WFNS (<3 or ≥3) patient's consciousness at inclusion
Daily dose of catecholamine	Presented graphically with 95% CI, per group			
Daily minimum and maximum natremia	Presented graphically with 95% CI, per group			
Daily urine output	Presented graphically with 95% CI, per group			

Unless otherwise stated, all analyses will be conducted on the Intention to treat population: includes all aSAH patients randomized.

** Adjustments for all listed analyses unless otherwise specified

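### The D7 and D14 angiographic model omits the vasospasm grade read on the inclusion CTA, and the SAP gives no rule for deaths in the imaging outcomes

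*SAP*

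**What the plan says.** **Outcome.** Section 5.1.3 c) defines it this way: "angiographic success will be assessed by the evaluation of vasospasm severity on inclusion, D7 and D14 (if available) CTA". The arterial narrowing is "evaluated on a semi-quantitative scale as: absent, light, mild, moderate or severe", each reading being made against the admission CTA. The inclusion grade is therefore collected on the same scale as the follow-up grades.

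**Model.** Section 5.2.3: "The analysis of angiographic successes at day 7 and 14 will be performed considering (ordinal) proportional odds models", with the covariate set of the primary model. Section 5.2.1 fixes that set, besides treatment arm, as "the center, the initial WFNS score dichotomized as <3 vs ≥ 3 and the patient's consciousness at inclusion". Table 1 repeats it: the angiographic row reads "Ordinal logistic regression model" and its adjustment column lists the same three factors. The inclusion grade appears in neither place.

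**Availability and deaths.** Section 1.2.3 makes imaging conditional, for example "on cerebral necrotic volume assess by magnetic resonance imaging (MRI) between 3 and 6 months following aSAH (if available", and D14 imaging carries the same condition. Section 5.2 makes intention to treat the default population. Section 5.3 prescribes multiple imputation for missing data in general, without limiting it to the primary outcome. Nothing says how a patient who dies before D7, D14 or the MRI enters the imaging analyses. For EQ-5D the SAP does address this: section 5.1.2 gives the deceased the lowest score where non-survivors are included, and Table 1 adds an analysis without them.

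**Inference.** Section 3.1 reserves p-values for primary and secondary outcomes, so the imaging outcomes, which are tertiary, get none.

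**The concern.** The angiographic outcomes are the plan's direct evidence on whether the drug opens the vessels. How narrow the arteries were at inclusion plausibly predicts how narrow they are a week or two later. A baseline reading of the outcome itself, already collected, is the obvious covariate, and the outcome definition mentions it. Leaving it out gives up precision at no saving.

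The second issue is death. Vessel calibre at D14 or infarct volume at 3 to 6 months does not exist for a patient who has died. If the SAP does not say what is compared, the analyst must choose. Section 2.4 holds back unblinding only until the primary and secondary analyses are complete, so the choice for a tertiary outcome could be made with the allocation known.

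**Working it through.** **The plan's own figure.** The SAP gives no power or precision figure for imaging. Its trial size serves below as the largest possible number scanned, so it was checked first. With 35% vs 50%, two-sided 5%, 80% power and a mean proportion of 0.425:

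n per arm = [1.96·√(2·0.425·0.575) + 0.842·√(0.35·0.65 + 0.50·0.50)]² / 0.15² = 169.3, so 170 per arm and 340 in total.

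340/0.95 = 358, which the SAP rounds up to 360. The figure reproduces and is not in dispute.

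**Cost of omitting the grade.** All inputs here are assumptions, because the SAP supplies none:
- Latent severity at follow-up is correlated r with severity at inclusion and shifted by 0.30 SD in the treated arm.
- Follow-up severity is cut into five grades of about 20% each in the control arm.
- Inclusion severity is cut into four grades, since everyone enters with confirmed vasospasm and the lowest grade should not occur. It is entered as a linear score.
- A proportional-odds model is fitted with and without the inclusion grade, 400 runs per setting. Centre, WFNS and consciousness are not simulated, so r stands for the correlation left after them.

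| r | N scanned | Power without grade | Power with grade | Difference (points, unrounded) |
|---|---|---|---|---|
| 0.2 | 340 | 82% | 81% | −1 |
| 0.3 | 340 | 74% | 79% | +4 |
| 0.5 | 340 | 75% | 84% | +9 |
| 0.7 | 340 | 74% | 91% | +17 |
| 0.5 | 240 | 60% | 69% | +9 |

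The Monte Carlo standard error is about √(0.75·0.25/400) = 2.2 points. In the N = 340 rows, power without the grade does not depend on r, so 82, 74, 75 and 74 estimate one quantity and the 82 is high by chance. The two models in a row share the same simulated data, so the comparison should be made along rows.

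**The same gain as interval width.** With no p-value, width matters more than power. For a linear covariate on the severity scale, width shrinks by the factor √(1 − r²): 0.98 at r = 0.2, 0.95 at 0.3, 0.87 at 0.5 and 0.71 at 0.7. These factors are the best case, because a four-grade reading carries less information than the underlying severity. In a proportional-odds model the gain takes another form. The standard error of the log odds ratio does not fall; the adjusted estimate moves away from zero relative to it.

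**Deaths.** A survivor-only comparison was simulated with no treatment effect on severity. Mortality rates and the link between death and severity are assumed.

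| Deaths, arm A vs arm B | Death unrelated to severity | Death odds ×2.7 per SD of severity |
|---|---|---|
| 10% vs 10% | 0.97 | 0.99 |
| 15% vs 10% | 1.00 | 0.92 |
| 20% vs 10% | 0.99 | 0.86 |

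Entries are odds ratios for a worse grade, arm A against arm B. The four settings with equal or unrelated deaths should give 1.00; their spread of 0.97 to 1.00 shows the simulation noise.

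**The case against.** **The outcome may already use the inclusion grade.** Each grade is relative to the patient's own admission scan, and the definition names the inclusion reading, so a change from inclusion may be intended. But the admission scan is a reference diameter, which is different from the severity of vasospasm at inclusion. Neither section 5.2.3 nor Table 1 describes a change outcome.

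**Nothing is biased, and nothing is tested.** Both points stand. Randomisation protects the comparison whether or not the grade is in the model, so it would be wrong to say that the follow-up grade alone cannot measure a treatment effect. Without p-values the loss is one of precision. The size of r is also unknown: all patients enter with vasospasm, the restricted range may lower r, and at 0.2 there is essentially no gain.

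**A reader might infer that only patients alive and scanned are analysed, which would favour the arm with more deaths.** The SAP does not support this. Its default population is intention to treat and its imputation rule is general; the availability wording is not an exclusion rule. The direction of bias also needs unequal mortality and deaths concentrated in severe vasospasm, and the SAP shows neither. What stands is that the plan is silent, and that its general imputation rule, taken literally, covers patients who have died.

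**A reader might infer that the MRI outcome is unadjusted.** In Table 1 the adjustment cell for "volume of cerebral necrosis on MRI done between 3 and 6 months" is blank, but the column's footnote applies the adjustments to all listed analyses unless otherwise specified. The cell is ambiguous and nothing here rests on it.

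**Ranking death worst mixes mortality with vessel calibre.** This is fair. Mortality is analysed separately, and a declared survivor-only estimand is legitimate.

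**Conclusion.** The main point holds as one of efficiency. The D7 and D14 models leave out a baseline reading that the SAP collects on the same scale and names in the outcome definition. Under a 0.30 SD shift and 340 scanned, including it adds nothing at a correlation of 0.2, about 4 points of power at 0.3, 9 at 0.5 and 17 at 0.7. Shift, correlation and number scanned are all assumptions.

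The secondary point holds as a gap: there is no stated handling of death for the CTA or MRI outcomes. Under a survivor-only analysis the spurious odds ratio would be about 0.86 to 0.92 if mortality differed by 5 to 10 points and depended strongly on severity, and about 1.0 otherwise.

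Both concern tertiary outcomes without p-values. The primary analysis and its conclusion are untouched.

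**What to change.** 1. In section 5.2.3 and in the angiographic row of Table 1, add the inclusion CTA vasospasm grade as a covariate in the D7 and D14 proportional-odds models, and say whether it enters as a linear score or as categories.
2. In section 5.3, state that scans are not imputed after death.
3. For CTA grade and MRI volume, declare the estimand: either survivors only, or death placed in a category worse than any scan result. Keep the other as a sensitivity analysis.
4. Report by arm the number scanned at each time point and the reasons for no scan. Section 5.3 already promises frequencies of missing data, but not by arm or by reason.

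The cost is SAP wording, plus recording the reasons for absent scans if these are not already captured; the inclusion grade is part of the planned assessment. Item 1 costs one model parameter as a linear score, or up to three as four categories. The changes should be made before database lock, and in any case before unblinding, because a rule for deaths chosen with the allocation known would carry little weight.
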